**Physiological Reactivity and Psychosocial Functioning in Pediatric  
Patients with Gastrointestinal Disease**

NCT05202418

Date: April 21, 2023  
IRB00085974

1. Title Page:

- Full study title: Physiological Reactivity and Psychosocial Functioning in Pediatric Patients with Gastrointestinal Disease
- Short study title: Stress in IBD
- Name, Title(s), and Department of Principal Investigator
  - [name], Associate Professor of Pediatrics
- Sponsor(s): Children's Healthcare of Atlanta and NIH, NIDDK, EPEX 52353, EPEX 70844
- Protocol version number and version date
  - Version 13
  - April 21, 2023

2. External (non-Emory) Collaborators (if applicable):
  - GI Care for Kids and Children's Healthcare of Atlanta. Letter of Support uploaded 1/26/2022. No other IRB review
3. Precis/Abstract: A brief (usually 400 words or fewer) description of the study objectives, population, design, and outcome measures

Similar to other chronic stressors, diagnosis with a chronic illness places youth at risk for adverse psychosocial outcomes. Inflammatory bowel diseases (IBD), Crohn's disease, ulcerative colitis, and indeterminate colitis, are chronic, immune-mediated diseases of the gastrointestinal tract characterized by unpredictable remissions of disease activity followed by relapses of symptoms. Increased risk for developing anxiety disorders and depression has been documented in youth with IBD. Individual differences in physiological reactivity may affect patients' risk for developing psychosocial difficulties within the context of chronic stress. The aim of the current study is to test whether differences in psychophysiological reactivity serve as risk factors in the relationship between clinical disease activity in youth newly diagnosed with IBD and psychosocial adjustment problems.

Up to 56 additional youth with IBD will be enrolled in a coping skills treatment to test the effectiveness of a cognitive behavioral intervention including biofeedback to reduce anxiety and depression and disease symptoms.

4. Introduction and Background: A summary of the primary hypothesis, purpose, scholarly rationale, and prior literature.

Similar to other chronic stressors, diagnosis with a chronic illness places youth at risk for adverse psychosocial outcomes. Inflammatory bowel diseases (IBD), Crohn's disease, ulcerative colitis, and indeterminate colitis, are chronic, immune-mediated diseases of the gastrointestinal tract characterized by unpredictable remissions of disease activity followed by relapses of symptoms including abdominal pain, diarrhea, rectal bleeding, weight loss, growth and pubertal delay, fever, fatigue, and arthritis (Mackner, Sisson, & Crandall, 2004). Approximately 25 to 30% of patients have onset of symptoms before the age of 18 years, making IBD one of the most prevalent childhood chronic illnesses (Malaty, Fan, Opeku, Thibodeaux, & Ferry, 2010).

Increased risk for developing anxiety disorders and depression has been documented in youth with Crohn's disease (Loftus et al., 2011). Compared to parents of healthy adolescents, parents of adolescents with IBD rated their adolescents as experiencing greater difficulties with anxiety and/or depression on the Child Behavior Checklist (Mackner et al., 2013). An early study, limited by a small sample size of 20 youth with IBD, found higher rates of self-reported depressive and parent-reported internalizing symptoms for youth with IBD compared to a healthy control group (Engstrom, 1999). In a recent meta-analytic review of psychosocial adjustment, youth with IBD were found to experience higher rates of depressive disorders as measured via diagnostic interview when compared to youth with other chronic illnesses (odds ratio = 5.80) (Greenley et al., 2010).

Although some research has found higher levels of disease activity to relate to greater depressive symptoms, the overall relationship between disease activity and emotional functioning has been mixed, suggesting that additional individual differences need to be considered in addition to illness related factors when predicting emotional outcomes (Mackner & Crandall, 2007). Maternal depression, stressful life events, family dysfunction, and steroid usage have been shown to relate to higher rates of depressive symptoms (Burke, Neigut, Kocoshis, Sauer, & Chandra, 1994; Mrakotsky et al., 2005). Additional risk factors for the development of psychosocial difficulties need to be identified to identify moderators of outcome above and beyond disease activity. Individual differences in physiological reactivity may affect patients' risk for developing psychosocial difficulties within the context of chronic stress. Physiological reactivity, which broadly refers to bodily reactions in response to a stressor, varies with regards to intensity and threshold for activation between individuals. When presented with a stressor, activity in the sympathetic nervous system (SNS) and hypothalamic-pituitary-adrenal axis (HPA) increases in preparation for managing the stressor (Chida & Hamer, 2008). Bodily tissues including the heart, vasculature, and adrenal medulla are activated by the SNS, resulting in consistent physiological responses that can be measured to quantify physiological reactivity. In humans, stress processing can be measured through complementary modes including heart rate variability (HRV) and skin conductance (SC). HRV and SC are non-invasive, easy to administer measures of the ANS suitable for pediatrics. HRV refers to fluctuation in the interval between consecutive heartbeats and is a product of the activating SNS and the inhibitory parasympathetic nervous system. Low HRV reflects reduced parasympathetic cardiac activity and is indicative of ANS rigidity and increased emotional reactivity to stress. High HRV is more adaptive, reflecting flexibility within the ANS and emotional responsivity (Walker et al., 2017). SC is the electrodermal activity (electrical impulses on the surface of the skin) produced by sweat glands that are stimulated by the SNS (Cummings, El-Sheikh, Kouros, & Keller, 2007). Skin conductance during periods of physical, cognitive, or emotional stress can be compared to baseline periods to obtain skin conductance level reactivity (SCLR), which has been shown to be a stable construct within individual across time and situation (El-Sheikh, 2007). SCLR is related to emotional and behavioral functioning, with higher reactivity most typically related to internalizing problems, and lower reactivity related to externalizing problems (Raine, Venables, & Williams, 1990).

In youth affected by non-medical chronic stress (e.g., family conflict, trauma history), measures of autonomic dysfunction have been used to explain why some individuals have worse psychological and physical outcomes compared to others exposed to similar levels of chronic stress (Cummings et al., 2007; El-Sheikh, 2005). Results support autonomic dysfunction as a vulnerability factor for adjustment problems within the context of chronic environmental stress.

In addition to the observational study, we will conduct a pilot intervention targeting autonomic dysfunction through a biofeedback enhanced coping skills treatment delivered virtually over 6-sessions.

## 5. Objectives: The primary and secondary aims and outcome measures.

Wave 1. Used to refer to originally approved protocol that has been ongoing.: The aim of the current study is to test whether greater skin conductance reactivity or SCLR will serve as a risk factor in the relationship between clinical disease activity in youth newly diagnosed with IBD and psychosocial adjustment problems. Findings will extend previous research that has identified SCLR as a vulnerability factor for children's adjustment problems within the context of family stress to youth with chronic illness.

Additional outcome measures will include self-report measures of anxiety and depression and psychological functioning.

Wave 2:

Objective of Wave 2 data collection is to evaluate associations between psychophysiological reactivity (skin conductance reactivity and heart rate variability) and systemic inflammation (C-reactive protein levels) with levels of anxiety, depressive, and disease symptoms in youth with IBD. Patients with IBD will then be followed longitudinally for a total of six data collection points across 24-months.

Intervention:

**Procedures.** We will enroll participants with IBD (n=56 total) in a biofeedback enhanced cognitive behaviorally based coping skills treatment. Participants will be randomized to biofeedback enhanced treatment (n=28 for IBD) or wait-list control (n=28 for IBD). Autonomic reactivity in response to stress induction and coping strategies will be measured at time of random assignment, at treatment end, and at 2-months follow-up to compare to wait-list control participants completing assessment only (n=28 for IBD). Treatment will consist of a 6-visit group intervention conducted online, via Emory zoom. Groups will include 5-8 patients. Groups will meet approximately each week for 6 weeks. I will train advanced PhD students in clinical psychology to assist me in delivering the treatment protocol. Trained research assistants who are not delivering the treatment will conduct all assessments. Sessions will include brief, daily homework to facilitate mastery that is developmentally tailored to youth (e.g., practice skills with support from phone or tablet apps). We anticipate that following treatment, participants will demonstrate statistically significant decreases in autonomic reactivity compared to wait-list control participants. Wait-list Control: Participants randomized to the wait-list control group will complete the same measures of lifetime stress, autonomic reactivity, depression, anxiety. The identical treatment will be offered to control participants after the 6-week time point.

Content of treatment will include:

Biofeedback Enhanced Coping Skills Treatment Protocol		Treatment Targets			
Session Content		Coping with illness	Anxiety Symptoms	Depressive Symptoms	Autonomic Dysfunction
1	Disease education; Goal Setting	X			
2	Deep breathing; Guided imagery; Progressive muscle relaxation	X	X		X
3	Biofeedback		X	X	X
4	Mindfulness-based exposure to negative emotions; Biofeedback		X	X	X
5	Pleasant activity scheduling; Biofeedback practice	X		X	
6	Biofeedback Maintenance Plan		X	X	X

6. Study design and methods:

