**Intervention:** As a follow-up to our observational studies described above, we have developed a biofeedback enhanced cognitive behavioral therapy to address symptoms of psychophysiological reactivity and anxiety and depression. We plan to enroll up to 56 patients with IBD in this intervention. Participants will be randomized to biofeedback enhanced treatment (n=28 patients with IBD) or wait-list control (n=28 patients with IBD). Autonomic reactivity in response to stress induction, symptoms of anxiety and depression, and coping strategies will be measured at time of random assignment, at treatment end, and at 2-months follow-up to compare to wait-list control participants completing assessment only (n=28 patients with IBD). Patients will also rate their disease symptoms and measures of clinical disease activity will be collected via chart review.

Potential participants will be recruited based on patients with IBD for psychological intervention and advertising through patient email listserves.

Treatment will consist of a 6-visit group intervention conducted via Emory zoom. Groups will include 5-8 patients each. I will train advanced PhD students in clinical psychology to assist me in delivering the treatment protocol. Trained research assistants who are not delivering the treatment will conduct all assessments. Sessions will include brief, daily homework to facilitate mastery that is developmentally tailored to youth (e.g., practice skills with support from phone or tablet apps). We anticipate that following treatment, participants will demonstrate statistically significant decreases in autonomic reactivity compared to wait-list control participants. Wait-list Control: Participants randomized to the wait-list control group will complete the same measures of lifetime stress, autonomic reactivity, depression, anxiety. The identical treatment will be offered to control participants after the 6-week time period.

7. If applicable: if data/samples collected for this study will be saved/banked/archived for future use, describe plans, who may use the material, and for what purposes (may require a separate repository-specific IRB submission).

Wave 1 and 2 observational research:

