In the cross-sectional comparison of IBD patients with age-sex-matched controls, measures of psychophysiological and immune functioning and levels of anxiety, depressive, and disease symptoms will be summarized using standard descriptive statistics. Differences between groups (IBD vs. control) will be made using paired t-test or Wilcoxon signed rank tests to account for paired samples. Linear models will be used to examine the relationship between ANS and neuroimmune function with levels of anxiety, depression and disease symptoms. Specifically, models will include the main effect of group, the main effect of predictor (e.g., physiological reactivity or CRP), and the interaction between group and predictor. The interaction serves as the statistical test to determine if the correlation between predictor and outcome (e.g., anxiety, depression, etc.) differs between IBD patients and controls.

Intervention: Primary goals of the intervention are to establish the feasibility and acceptability of a RCT of enhanced biofeedback to improve autonomic reactivity and reduce levels of depression, anxiety and clinical symptoms in pediatric patients with IBD. Feasibility measures including consent rates, completion/retention rates, and treatment satisfaction ratings will be summarized using counts and percentages or means and standard deviations, as appropriate. Changes in clinical scores (anxiety, depression, and clinical symptoms) and autonomic reactivity from baseline, to end of treatment, and 2 months post treatment will be summarized within groups at each study time-point. The changes in the measures *within* and *across* groups will be analyzed using a two-factor repeated measures analysis of variance model

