(rmANOVA). Models will include the main effect of group, the effect of time and the group X time interaction term. Other baseline covariates including age, disease severity, and other clinical characteristics may be included in the models. Data will be modeled using the *MIXED* procedure in SAS which allows for use of all outcome data, even in the presence of missing data. Differences in group means will be calculated and presented along with 95% confidence intervals. Effect sizes will also be calculated to further describe the degree of difference between groups. Appropriate modeling assumptions will be verified prior to analysis and analysis will follow the intention to treat principal. In exploratory analyses, we will determine whether reductions in anxiety, depression and stress are mediated by changes in autonomic reactivity and coping strategies by exploring the direct and indirect effects of autonomic reactivity and coping strategies on perceived stress, anxiety and depression. For each outcome of interest (e.g., depression), an estimation of the mediation effect will be calculated using the difference in the regression coefficients ( $\beta_1 - \beta_2$ ) obtained from the two linear regression models with and without the mediator (i.e., skin conduction measure or HRV). Bootstrapping (5000 samples) will be used to obtain the empirical distribution of the mediation effect and test the null hypothesis that the difference-in-coefficients ( $\beta_1 - \beta_2$ ) is zero. This method has superior statistical power for relatively small sample sizes and does not require a large effect size.

12. Data and Safety Monitoring and Reporting: The IRB will be notified of any unexpected, adverse events. As this study is low risk, no such events are anticipated. Any adverse events associated with venipuncture will be monitored by the PI and reported to site medical doctors, [name] and patients' primary physician at GI Care for Kids, as well as Emory IRB.

13. Confidentiality:

- Privacy will be protected by handling all in-person conversation and study procedures in private exam rooms.

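### Wait-list controls may be treated before the 2-month follow-up, so that between-arm comparison can understate the effect of treatment versus no treatment

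*Combined protocol and SAP*

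**What the plan says.** Section 5 (Intervention, Procedures) measures both arms at random assignment, "at treatment end, and at 2-months follow-up to compare to wait-list control participants completing assessment only (n=28 for IBD". Section 6 (Intervention) repeats this: "at treatment end, and at 2-months follow-up to compare to wait-list control participants completing assessment only (n=28 patients with IBD". On either reading, controls are untreated at the 2-month visit.

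The same two paragraphs describe the wait list differently. Section 5: "The identical treatment will be offered to control participants after the 6-week time point". Section 6: "The identical treatment will be offered to control participants after the 6-week time period". The course is short: "Groups will meet approximately each week for 6 weeks".

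Section 11 dates the follow-up from the end of treatment. Changes in clinical scores and "autonomic reactivity from baseline, to end of treatment, and 2 months post treatment will be summarized within groups at each study time-point". For the between-arm analysis it specifies a repeated measures model on the intention-to-treat principle, using all outcome data: "Models will include the main effect of group, the effect of time and the group X time interaction term". Group differences with 95% confidence intervals and effect sizes are to be reported. Section 11 also sets the priority: "Primary goals of the intervention are to establish the feasibility and acceptability of a RCT of enhanced biofeedback".

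The documents do not say when controls may start, how many are expected to, or how their data are handled once they have. They do not name the visit that tests the treatment effect.

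**The concern.** The comparator cannot be relied on to be untreated at a visit that falls more than eight weeks after the same treatment is offered to it. If controls start before that visit and the treatment works, as the protocol anticipates, the two arms converge. The 2-month difference, its confidence interval and its effect size then no longer estimate treatment versus assessment alone.

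Two readings could go wrong. A lasting benefit could look, in the between-arm difference, as if it had faded, when in fact controls had caught up. The group-by-time test could be significant for patterns with quite different meanings. The effect sizes from this pilot are also what a later trial might be planned on, and a diluted 2-month value would mislead it.

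**Working it through.** **Inputs from the documents.** 28 per arm (28 + 28 = 56); six sessions about a week apart; offer to controls after week 6; follow-up two months after treatment; model with group, time and group by time. The plan gives no effect size, SD, significance level or power for the intervention, so it has no figure of its own to reproduce.

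**Timeline.** Two months is 2 × 365.25 / 12 / 7 = 8.7 weeks, so the follow-up falls at about 6 + 8.7 = week 14.7. Six weekly sessions span five intervals, so the latest start that fits all six before the visit is 14.7 − 5 = week 9.7. Starts at weeks 10, 12 and 14 allow five, three and one sessions. Sessions are only approximately weekly, so these dates are approximate too.

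**Assumptions.** True effect d = 0.6 SD; correlation between visits ρ = 0.5 (compound symmetry); two-sided 5% level; a share u of controls treated before the visit, each with full benefit. The expected between-arm differences at the three visits are then (0, d, d(1 − u)).

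**Formulas.**
- 2-month change contrast: SE = √(2(1 − ρ)) × √(2/28) = 0.267; noncentral t.
- Group main effect: expected value (0 + d + d(1 − u))/3; SE = √((1 + 2ρ)/3) × √(2/28) = 0.218; noncentral t.
- Group by time: F(2, 108) with λ = (28/2) × Σ(m − mean)² / (1 − ρ), where m are the three visit differences.

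| Controls treated (u) | 2-month difference, SD | Power | Group main effect, SD | Power | λ, group by time | Power |
|---|---|---|---|---|---|---|
| 0% | 0.60 | 60% | 0.40 | 44% | 6.72 | 62% |
| 25% | 0.45 | 38% | 0.35 | 35% | 5.46 | 53% |
| 50% | 0.30 | 20% | 0.30 | 27% | 5.04 | 50% |
| 80% | 0.12 | 7% | 0.24 | 19% | 5.64 | 54% |
| 100% | 0.00 | 5% | 0.20 | 15% | 6.72 | 62% |

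The end-of-treatment change contrast has 60% power in every row. The main effect starts at 0.40 SD because it averages in baseline, where no difference is expected; only the fall from 0.40 is due to crossover. A 20,000-run simulation with uptake drawn for each control, at u = 0, 50, 80 and 100%, agreed with the powers above to within 0.01.

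**Why the interaction test is hard to read.** With untreated controls and a lasting effect the profile is (0, 0.6, 0.6), with mean 0.4 and sum of squares 0.16 + 0.04 + 0.04 = 0.24. With full crossover and a lasting effect it is (0, 0.6, 0), with mean 0.2 and sum of squares 0.04 + 0.16 + 0.04 = 0.24. The test cannot tell the two apart.

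**Sensitivity.** At d = 0.4, 2-month power falls from 31% with no uptake to 11% at 50% uptake; at d = 0.8, from 84% to 31%. Partial benefit scales the loss: if treated controls show half the effect, 50% uptake gives 0.6 × (1 − 0.5 × 0.5) = 0.45 SD and 38% power.

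**The case against.** The strongest reply is that little depends on the 2-month between-arm difference. Feasibility and acceptability come first, and the consent, retention and satisfaction summaries do not use it. The protocol's one directional efficacy statement concerns decreases following treatment, which reads most naturally as the end-of-treatment contrast. Section 11 already plans within-group summaries at every visit, and these would show the biofeedback arm holding its gain while controls improve later. The group main effect is a term in the model and is not named as the test. The interaction test loses at most about 13 points of power (62% to 50%) and nothing at full crossover. Uptake and timing are assumed, and the need to fill groups of 5 to 8 may delay controls. The power figures also ignore clustering within therapy groups.

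Much of this stands, and it narrows the harm. A careful reader of the within-group summaries would not be misled; the risk lies in the 2-month difference, interval and effect size read on their own. The main-effect column matters only if someone uses that term as a test of treatment. Clustering could change the powers, but not the dilution of the expected difference.

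It does not remove the problem. Sections 5 and 6 both include the 2-month visit in a comparison with controls who have had assessments alone, and both undercut it with the week-6 offer. Forming groups may slow uptake, but the plan does not require a delay.

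**Conclusion.** The concern holds. As written, the plan cannot guarantee an untreated comparator at 2 months, and it does not say what the 2-month difference estimates. To the extent controls are treated by then, that difference is biased toward zero for treatment versus no treatment, and the group main effect shrinks with it. The direction requires that the treatment works and that some controls start before the visit. The size cannot be fixed from the documents: with d = 0.6, ρ = 0.5 and full benefit in treated controls, the expected 2-month difference runs from 0.60 SD at no uptake to 0.30 at half and zero at full uptake.

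The 2-month difference is still a valid intention-to-treat estimate of immediate versus delayed treatment, and the end-of-treatment contrast is sound. The feasibility goals are untouched. What needs correcting is the secondary efficacy conclusion drawn at 2 months.

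**What to change.** In section 11:
- Name the end-of-treatment contrast from the group-by-time model as the between-arm test of treatment effect, and state that the group main effect is not a test of treatment.
- Keep the 2-month visit in the model, but report its between-arm difference and 95% confidence interval as immediate versus delayed treatment, alongside the number of controls who had started and the sessions they had attended before the visit.
- Use the within-group summaries already planned to describe durability in the biofeedback arm.

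In sections 5 and 6, correct the description of controls at the 2-month visit to match the week-6 offer.

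The cost is wording, plus recording control start dates and attendance. The trial then makes no randomised claim about durability, which the written schedule does not support anyway.

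The alternative is to hold the offer until after the 2-month visit. That keeps a randomised durability comparison, but makes young people who screened positive for depression or anxiety wait about 9 more weeks (14.7 − 6 = 8.7). That trade-off is for the sponsor.
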